The Effects of VR Interactive Games on Balance and Quality of Life Enhancement for Elderly in the Community

> Unique Protocol ID: N202210004 Document Date: June 26, 2023

Abstract

Thesis title: Examining the effectiveness of a virtual reality interactive game on physical fitness and quality of life in community-dwelling elderly people

Name of degree and program: Master's program in Long-term Care, Taipei Medical University

Graduate student: [name]

Thesis directed by: [name], Associate [name] Ph.D. Program in Gerontology and Long-term Care, Taipei Medical University

Background: Currently, community exercise courses are mostly guided by nurses and there are few opportunities for participating elderly people to interact with others during exercise. An interactive game was developed to allow elderly people participating in community activities to use game feedback to increase enjoyment and competitiveness in team games. Besides improving physical fitness, and increasing motivation and willingness to continue participating in exercise, this can also improve the quality of life.

Objective: To examine whether a virtual reality interactive game exercise can help improve the physical fitness and quality of life of elderly people. Methods: Elderly people aged 65 years and above who participate in community activities were recruited and randomized into the experimental group and control group. The experimental group completed 36 episodes of exercise intervention using the interactive game,

I

spread over 12 weeks, while the original routine exercise was used as the course content in the control group. Both groups underwent 36 episodes of intervention of one hour each time, thrice a week for 12 consecutive weeks. Assessments of functional physical fitness and satisfaction with quality of life were performed before and after intervention and the statistical significance was set as p < 0.05.

Results: After 36 weeks of virtual reality interactive game interaction, the post-test scores for 2-minute step test (p<0.001), right chair sit-and-reach test (p=0.010), left chair sit-and-reach test (p=0.002), psychological quality of life (p=0.033), and environmental quality of life (p=0.048) of the experimental group were all significantly higher than those of the control group.

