From the synthesis of the above literature, it is evident that the primary goal of "healthy aging" is to maintain and enhance the physical function of the elderly population, enabling them to lead happy, satisfying, and fulfilling lives. The decline in functional abilities and the increase in sedentary behavior among the elderly are closely related, making it crucial to address how to maintain their physical function, prevent or delay disability, reduce medical and social costs, and improve quality of life. Regular exercise is recognized as the best strategy for improving the sensory-motor system and maintaining balance to prevent falls. By designing group activities that increase the atmosphere of group activities and incorporating game feedback and interactive processes with others, participants can become highly engaged and focused within the social group. They can feel relaxed, relieved of stress, and experience mood changes during facility activities. This increases motivation and willingness to continue participating in exercise and accomplishing tasks during the game, boosting confidence among the elderly and consequently enhancing their quality of life by redefining the value and meaning of life.

Chapter 3: Research Methodology Section 1: Research Design

This study adopts an experimental design with a pre-test and post-test for two groups. Convenience sampling is utilized as the sampling method, and data collection is conducted through questionnaires and measurement evaluation scales. The research investigates the intervention of integrating VR interactive games to assist in improving balance function and lower limb strength among the elderly, thereby enhancing their quality of life. The proposed intervention research framework is depicted below (Figure 2).

[figure not shown]

Figure 2 Research framework diagram of using virtual reality interactive games to improve balance and quality of life of community elders

Section 2: Research Site, Participants, and Ethical Considerations Research Site:

This study will be conducted among community-based activities and voluntary participants aged 65 and above.

Research Participants:

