During the game, coins and meteors appeared in eight directions on the screen. Participants earned points by moving their bodies to collect coins and avoid meteors. After each session, scores were summarized and ranked to motivate participants. The recorded body angle data were stored in the backend cloud platform for post-game analysis.

During the VR interactive game training, participants were instructed to stand with their feet shoulder-width apart and move their upper bodies

according to the music and game screen cues. They were encouraged to stretch and bend their arms along with their bodies' forward, backward, left, and right movements to increase upper body activity and effectively maintain body balance. Participants with weaker lower limbs could use the backrest of a chair for support to prevent accidents.

Figure 3 Research equipment laptop and touch tablet connected to projecto

Figure 4: Startup screen of virtual reality interactive game system

Figure 5 Virtual reality interactive game activity screen

Figure 6: Photos of the elderly participating in activities and using chair backs to prevent falls Control Group Intervention

The control group maintained their regular aerobic exercise regimen, led

by a fitness instructor, three times a week for 1 hour per session. The

structure of each session was as follows:

Warm-up Exercises: 10-15 minutes

Main Exercise Activity: 30 minutes

Cool-down Exercises: 5-10 minutes, including a 10-minute break Over the course of 36 sessions, the control group participated in a variety of exercises, including resistance band training for 12 sessions, chair yoga for 12 sessions, and aerobic exercise for 12 sessions. Apart from these structured exercise sessions, both groups did not engage in any other physical activities during the 36-week period.

Figure 7 Photos of elders in the control group participating in activities

Section 5 Evaluation Tools

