This study involved the intervention of the experimental group using virtual reality interactive games, while the control group underwent exercise interventions led by original instructors. Both groups participated in modal rate-intensity sessions three times a week for 12 weeks, totaling 36 sessions. Testing was conducted befor and three months after the completion of the program. A total of 84 participants were recruited from two community care activity centers in Taipei City, but 14 participants were excluded due to personal reasons or inability to consistently monitor data due to illness. Ultimately, data from 70 participants who completed at least 30 sessions were analyzed.

Regarding participant attrition, the experimental group initially recruited 35 participants. However, during the 12-week, 36-session program, five participants were absent for over one-third of the sessions (12 sessions) due to health issues or personal preferences, rendering their data unusable. The experimental group experienced a dropout rate of 14.28%. The control group initially recruited 35 participants, but only 33 completed the post-intervention assessment. Two participants were excluded from the analysis due to absence for over one-third of the sessions. The dropout rate for the control group was 8.57%. Both groups had dropout rates within the predetermined range of 15% set befor the study.

The study spanned 36 sessions from February 13th to May 31st, [insert year]. Data from participants who attended less than 12 sessions were

excluded from statistical analysis. Thus, statistical analysis was conducted on data from 30 participants in the experimental group and 33 participants in the control group.

Section 1: Participant Demographics

This study recruited a total of 70 participants, with 35 participants in both the experimental and control groups. Among them, 63 participants completed the entire study, with 30 participants in the experimental group and 33 participants in the control group. The average age of the experimental group (30 participants) was 77.7 years, with the majority being female (96.7%) and married (90.0%). See Table 4-1 for details. Assessment of demographic data in both groups showed no significant differences. Independent samples t-tests or Mann-Whitney U tests and chi-squared tests were used to analyze demographic data, revealing no significant differences between the two groups' demographic characteristics, as shown in Table 2.

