The results of ANCOVA analysis (Table 6) revealed that the post-test scores of the experimental group were significantly higher than those of the control group in five assessment outcomes, including the 2-minute step test (p < 0.001), right chair sit and reach (p = 0.010), left chair sit and reach (p = 0.002), psychological quality of life (p = 0.033), and environmental quality of life (p = 0.048). Additionally, the differences in fitness (except for the 30-second chair stand test) and quality of life had effect sizes (partial eta squared) ranging from 0.011 to 0.267, indicating moderate to substantial intervention effects. These results suggest that the intervention in this study was more effective in improving the aforementioned fitness and quality of life compared to regular community activities.

	StatisticsF /(p)	effect size (partial eta
		squared)
BMI	0.195 (0.661)	0.003
30 seconds sit and stand	0.015 (0.904)	0.000
The seat body bends forward (right)	21.154 (<0.001)	0.267
The seat body bends forward (left)	7.091 (0.010)	0.109
Get up and walk Around at 2.4 meters	10.294 (0.002)	0.151
Physiological quality of life	0.667 (0.418)	0.011
Psychological quality of life	0.956 (0.332)	0.016
Quality of social life	4.766 (0.033)	0.076
Environment quality of life	1.405 (0.241)	0.024
The seat body bends forward (right)	4.080 (0.048)	0.066

Table 6Post-test comparison between the experimental group and the

control group

Note: This analysis uses ANCOVA to control the pretest scores and other significant influencing factors

in the pretest. The control variables include: age, education level, and pretest scores of each variable.

Section 3: Analysis and Comparison of Quality of Life Questionnaire

Upon statistical analysis of pre-test and post-test scores (Table 7), it was found that in the experimental group, there was a difference of 0.4points in the physical domain (p = 0.202), no difference in the psychological domain (p = 0.008), a difference of 0.2 points in the social relationships domain (p = 0.500), and no difference in the environmental domain (p = 0.500). In contrast, in the control group, there was a difference of 0.4 points in the physical domain (p = 0.325), no difference in the psychological domain (p = 1.000), and no difference in the social relationships and environmental domains. The results indicate a significant change in the quality of life in the physical domain for the experimental group.

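### The Abstract claims randomisation but the readable Methods describe no allocation method, and the ANCOVA of this two-centre study leaves out centre

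*Combined protocol and SAP*

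**What the plan says.** The Abstract (Methods) says that elderly participants in community activities "were recruited and randomized into the experimental group and control group". In the readable text this is the only statement that this study allocated people at random.

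Chapter 3, Section 1 says "This study adopts an experimental design with a pre-test and post-test for two groups" and then "Convenience sampling is utilized as the sampling method". Sections 1 to 6 of that chapter, as far as they can be read, give no random sequence, unit of allocation, stratification or concealment, and do not name the number of centres.

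The number of centres first appears in Chapter 4: "A total of 84 participants were recruited from two community care activity centers in Taipei City". The same passage says that "the experimental group initially recruited 35 participants" and uses the same form of words for the control group. Under Control Group Intervention, "The control group maintained their regular aerobic exercise regimen"; Chapter 4 adds that the original instructors led it.

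The planned ANCOVA (Chapter 3, Section 6, item 2(d)) adjusts for the pre-test score only. For the reported ANCOVA, the note to Table 6 says "The control variables include: age, education level, and pretest scores of each variable". Centre is in neither model, and no table crosses arm with centre.

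The conclusions are causal. Chapter 5, Section 2 says that the VR programme did better than the usual centre classes, and Chapter 6 says that it improves fitness and quality of life.

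**The concern.** Two centres may differ in instructors, neighbourhood, participant mix and how the fitness tests are run. If people were randomised individually within each centre, such differences fall evenly on both arms in expectation, and leaving out centre costs only precision. If allocation followed centre in whole or in part, the same differences enter the arm comparison. Adjusting for age, education and pre-test removes only what those variables capture.

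The reader cannot tell which case applies, because the allocation method and the arm-by-centre counts are both missing. Whether the causal conclusions follow from the data depends on the answer.

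**Working it through.** **1. Was centre in the fitted model?** Inputs are the F values and partial eta squared in Table 6 and N = 63 (30 + 33) from Chapter 4. The row labels in Table 6 do not line up with the text, so I matched rows to outcomes by their p-values.

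Partial eta squared = F / (F + error df). With intercept, arm, pre-test, age and education (one df each), error df = 63 − 5 = 58.

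- 2-minute step: 21.154 / (21.154 + 58) = 0.267; stated 0.267.
- Left sit-and-reach: 10.294 / 68.294 = 0.151; stated 0.151.
- Right sit-and-reach: 7.091 / 65.091 = 0.109; stated 0.109.
- Psychological quality of life: 4.766 / 62.766 = 0.076; stated 0.076.
- Environmental quality of life: 4.080 / 62.080 = 0.066; stated 0.066.

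The other five rows agree too. One extra term (57 df) would give 0.271 for the step test, which does not match. The terms in the table note use up the degrees of freedom, so centre was not in the model.

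**2. What would adding centre do?**

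- Both arms in both centres: the term can be fitted and error df falls from 58 to 57.
- Each arm one centre: the centre indicator is the arm indicator, or one minus it. The two are collinear, and no model on these data separates them.

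**3. Do the baseline tables settle the question?** Inputs are Tables 2 and 3.

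- Age: pooled SD = √[(29×5.8² + 32×8.3²)/61] = 7.22; (77.7 − 74.4)/7.22 = 0.46 SD; stated p = 0.080.
- BMI: pooled SD = √[(29×3.5² + 32×3.8²)/61] = 3.66; (27.0 − 25.4)/3.66 = 0.44 SD; stated p = 0.077.
- High school or above: 6/30 = 20.0% against 17/33 = 51.5%; stated p for education = 0.014.
- Time per exercise session: stated p = 0.039.

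Tables 2 to 4 hold 19 distinct baseline tests. If they were independent, the chance of two or more below 0.05 is 1 − 0.95¹⁹ − 19×0.05×0.95¹⁸ ≈ 0.25. The imbalance is therefore compatible with randomisation. The tables also describe the 63 people analysed, not the groups as formed.

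**4. Sensitivity if each arm were one centre.** The documents give no intraclass correlation (ICC), so the values below are assumptions. Design effect = 1 + (m − 1)×ICC, with m = 2/(1/30 + 1/33) = 31.4. This gives 1.30 at ICC 0.01, 2.52 at 0.05 and 4.04 at 0.10. Each F is divided by the design effect and referred to 1 and 58 df.

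| Outcome | Reported p | ICC 0.01 | ICC 0.05 | ICC 0.10 |
|---|---|---|---|---|
| 2-minute step | <0.001 | 0.0002 | 0.005 | 0.026 |
| Left sit-and-reach | 0.002 | 0.007 | 0.048 | 0.12 |
| Right sit-and-reach | 0.010 | 0.023 | 0.099 | 0.19 |
| Psychological QoL | 0.033 | 0.061 | 0.17 | 0.28 |
| Environmental QoL | 0.048 | 0.082 | 0.21 | 0.32 |

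These are not corrected p-values. With one centre per arm there are no between-centre error df, so the table holds only if the ICC is treated as known. It does not apply if the arms were mixed within centres.

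**The case against.** The case for the authors is substantial, and most of it stands.

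- Convenience sampling says how people were found. It does not conflict with randomising them afterwards. The Abstract says outright that they were randomised, and the Methods call the design experimental. A reader might infer that the study was non-randomised, but the text supports only that the allocation method is not described.
- Nothing links arm to centre. A reader might take the separate recruitment figures and the continued usual class as a sign that each arm was one centre. Both also fit individual randomisation with a usual-activity comparator.
- Figures 2 and 8 and part of the end matter are not in the text available here. An allocation step could be drawn in either figure.
- Age and education, the first and third of the four imbalances above, are already covariates. Time per exercise session is not.
- If people were randomised individually within centres, omitting centre does not bias the arm effect.

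What remains is that centre is absent from both models, that arm by centre is not reported, and that the causal conclusions carry no condition on either.

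**Conclusion.** The point holds as a conditional one. Allocation is claimed but not described in the readable text, recruitment came from two centres, and the analysis leaves centre out; the exact match of Table 6 at 58 df confirms the last. If allocation was not random within centre, the arm effect is partly or wholly confounded with centre. The documents neither show nor exclude this, so no single corrected estimate can be given.

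A reader might also infer from the sensitivity table that the findings as a group would disappear. The table does not support that. Under the assumed ICCs the two quality-of-life results are the most fragile, while the 2-minute step result stays below 0.05 even at ICC 0.10. All of this applies only if each arm was one centre.

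This is a cheap and worthwhile improvement, not a demonstrated error in the results.

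**What to change.** 1. State in Chapter 3 how people were allocated: the method, the unit (person or centre) and any stratification. If a random sequence was used, describe it. If none was used, remove the word randomized from the Abstract.
2. Add a table of arm by centre, for those recruited and those analysed.
3. If both arms occur in both centres, add centre as a fixed factor to every ANCOVA, in the plan and in Table 6. This guards against centre differences or adds precision. If allocation was not random, self-selection within centre remains and should be stated as a limitation.
4. If each arm was one centre, say that the VR effect cannot be separated from the centre effect. Limit the Abstract, Chapter 5, Section 2 and Chapter 6 to an association.

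The cost is a table, some wording and, under item 3, a rerun with one fewer error df (58 to 57). Some results may become weaker. Under item 4 no rerun helps; the cost is a narrower conclusion.

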The sample size for this study is calculated using G-power 3.1.9.7 statistical software to determine the effect size. According to Cohen (1988), effect sizes are categorized as large (0.80), medium (0.50), and small (0.20). Since most research results have an effect size of 0.50, this study sets the criterion of at least a medium effect size. With α =0.05, statistical power (power)=0.80, and effect size set at 0.5, the estimated sample size is 60 individuals. Considering potential changes in the elderly or refusal to participate, a dropout rate of 15% is estimated. Therefore, a total of 70 elderly individuals from community-based activities will be recruited for this study. The inclusion criteria for this study are as follows: (1) aged 65 and above, (2) able to communicate in Mandarin or Taiwanese and willing to complete interviews or self-administered questionnaires, (3) no mobility impairments (e.g., stroke, Parkinson's disease, motor neuron diseases), (4) no severe cardiovascular diseases, (5) no degenerative joint diseases or acute attacks in the past three months, (6) lower limb joint surgery performed more than three months ago, and (7) no dizziness or any unstable health conditions that hinder exercise. During the study period, participants who do not engage in physical

activity for more than three weeks or have missing pre-test or post-test data will be excluded from the statistical analysis.

Ethical Considerations:

Prior to conducting the study, the research proposal will be submitted to the Institutional Review Board (IRB) for review and approval. Approval was obtained from the Taipei Medical University Joint Institutional Review Board (TMU-JIRB) on November 24, 2022, with the approval letter numbered N202210004 (see Appendix 1). This study aims to investigate the effects of VR interactive games as part of exercise prescriptions on the balance function and lower limb strength of elderly participants.

Section 3: Intervention Tools

Hardware Setup:

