After data collection, the collected data will be coded, documented, and analyzed using the Statistical Package for the Social Sciences (SPSS) 19.0 Chinese version software. Both descriptive and inferential statistics will be employed. A significance level of p < .05 will be used to determine statistical significance.

1. Descriptive Statistics:

Categorical variables of demographic data for both experimental and control groups will be presented as percentages, while continuous variables will be described using means and standard deviations.

2. Inferential Statistics:

(a) Independent t-test or Mann-Whitney U test:

Analyze the differences between the experimental and control groups in variables such as balance function, muscle strength, flexibility, cardiovascular capacity, and quality of life befor intervention. A Shapiro-Wilk test will be conducted to check for normal distribution. If the data is normally distributed, an independent t-test will be used; otherwise, the Mann-Whitney U test will be employed.

(b) Chi-Squared Test:

Analyze the homogeneity of basic demographic characteristics (age, gender, education level, marital status), exercise habits, duration of each exercise session, and experience of falling in the past year between the two groups.

(c) Dependent Samples t-test or Wilcoxon Signed Rank Test: Analyze the differences in variables such as balance function, muscle strength, flexibility, cardiovascular capacity, and quality of life within each group 之前 and after the intervention. A Shapiro-Wilk test will be conducted to check for normal distribution. If the data is normally distributed, a dependent samples t-test will be used; otherwise, the Wilcoxon signed rank test will be employed.

(d) ANCOVA Analysis using Intention-to-Treat Analysis:

ANCOVA will be employed to compare the post-test scores between the experimental and control groups while controlling for pre-test scores. This analysis will utilize intention-to-treat principles.

[figure not shown]

Figure 8. Flowchart of the application of virtual reality interactive games

to the lower limb balance of community elders

Research Results

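### The stated inputs (alpha 0.05, power 0.80, effect size 0.5) do not give 60 participants; an unadjusted two-group comparison needs 128 two-sided or 102 one-sided

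*Combined protocol and SAP*

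**What the plan says.** Chapter 3, Section 2 (Research Participants) says that the size was calculated in G-power 3.1.9.7. It fixes the effect-size scale, "According to Cohen (1988), effect sizes are categorized as large (0.80), medium (0.50), and small (0.20", adopts the medium value, and concludes: "statistical power (power)=0.80, and effect size set at 0.5, the estimated sample size is 60 individuals". Allowing for 15% dropout, the target becomes 70.

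The paragraph names no statistical test, no sidedness, no allocation ratio and no pre/post correlation. The rest has to be taken from elsewhere:

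- Design (Chapter 3, Section 1): "This study adopts an experimental design with a pre-test and post-test for two groups".
- Between-group outcome analysis (Chapter 3, Section 6(d)): "ANCOVA will be employed to compare the post-test scores between the experimental and control groups while controlling for pre-test scores".
- Significance (Chapter 3, Section 6): "A significance level of p < .05 will be used to determine statistical significance". This does not settle sidedness.
- Numbers analysed (Research Results): "Thus, statistical analysis was conducted on data from 30 participants in the experimental group and 33 participants in the control group".

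**The concern.** A two-group comparison at a medium standardised difference of 0.5 with 80% power is a standard calculation, and its answer is about twice 60. The paragraph presents 60 as the output of the inputs it lists, so a reader should be able to reproduce it, and cannot.

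This paragraph is the plan's only justification for the size of the study. If the 80% is taken at face value, a non-significant between-group result would be read as evidence against a medium effect. The 30-second chair stand test, for example, has F = 0.015 and p = 0.904 in Table 6, which reports F, p and partial eta squared but no adjusted difference or confidence interval. Whether that reading is safe depends on a correlation that the plan never gives.

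**Working it through.** **Inputs.** Alpha 0.05, power 0.80 and effect size 0.5 come from Chapter 3, Section 2. Two groups come from Chapter 3, Section 1. Equal allocation is an assumption, consistent with the 35 and 35 reported as recruited. Sidedness is not stated, so both are shown.

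**1. Attempt to reproduce 60 with two independent means.**

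Normal approximation, per group: n = 2(z_alpha + z_power)² / d².

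- Two-sided: 2 × (1.960 + 0.842)² / 0.25 = 62.8, so 63 per group and 126 in total.
- One-sided: 2 × (1.645 + 0.842)² / 0.25 = 49.5, so 50 per group and 100 in total.

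The exact calculation uses the noncentral t distribution with noncentrality d√(n/2) and 2n − 2 degrees of freedom:

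- Two-sided: 64 per group, **128** in total (power 0.801).
- One-sided: 51 per group, **102** in total (power 0.806).

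The stated 60 is 60/128 = 47% of the first and 60/102 = 59% of the second.

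**2. Other readings of the same inputs.**

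| Reading | Total N |
|---|---|
| Mann-Whitney (t-test n × π/3) | about 136 two-sided, 108 one-sided |
| Paired t-test, d = 0.5 | 34 two-sided, 27 one-sided |
| Two-group F test (ANOVA or ANCOVA), f = 0.25 (equal to d = 0.5) | 128 |
| Same F test, f = 0.4 | 52 |
| Same F test, 0.5 read as f | 34 |

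None gives 60.

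**3. What 30 per group provides without adjustment, d = 0.5.** Noncentrality is 0.5 × √15 = 1.94, on 58 degrees of freedom.

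- Power: 0.478 two-sided, 0.606 one-sided.
- With the 30 and 33 analysed: 0.496 two-sided.
- Difference detectable with 80% power, two-sided: d = 0.74 (30/30) or 0.72 (30/33).

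**4. The planned ANCOVA.** Adjusting for the pre-test score turns the effective difference into d/√(1 − r²), where r is the pre/post correlation. One degree of freedom is lost, leaving 57 at 30/30. The plan gives no r, so the values below are assumptions. All figures are two-sided.

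| Assumed r | Effective d | Power at 30/30 | Total N for 80% |
|---|---|---|---|
| 0 | 0.50 | about 0.48 | 128 |
| 0.5 | 0.58 | 0.59 | 98 |
| 0.7 | 0.70 | 0.76 | 68 |
| 0.8 | 0.83 | 0.89 | 48 |

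Power at 30/30 reaches 80% at r = 0.734 two-sided or 0.639 one-sided. At 30/33 the two-sided threshold is about 0.72.

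**5. Dropout step.** 60/0.85 = 70.6, so 71 against the stated 70. This step is consistent to within one person; the problem is the 60.

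**The case against.** The strongest reply is that 128 and 102 belong to a test the plan does not use for its outcome. Section 6(a) keeps the independent t-test and Mann-Whitney test for differences before the intervention. The planned between-group outcome comparison is the ANCOVA, and that is the analysis reported. Under ANCOVA, 60 is enough if the pre/post correlation is about 0.73, which is not far-fetched for fitness tests.

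The reported data give some support. The correlation can be backed out of Table 5 as (SD_pre² + SD_post² − SD_change²) / (2 × SD_pre × SD_post), matching rows to Table 4 by their pre-test values because Table 5's row labels are displaced. Control-group values run from 0.81 (2-minute step) to 0.99 (left sit-and-reach). Test-group values are 0.76 for the chair stand and 0.72 and 0.71 for sit-and-reach, but 0.49 for the up-and-go and only 0.11 for the 2-minute step: (20.7² + 25.7² − 31.2²) / (2 × 20.7 × 25.7) = 0.11.

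This part stands: 60 is not shown to be inadequate for the ANCOVA. It does not rescue the paragraph. The correlation is an extra input that the paragraph does not contain, and the paragraph does not mention ANCOVA. The values in Table 5 are results rather than planning inputs, and they fall on both sides of the threshold. A repeated-measures interaction with f = 0.25 also comes near 60 (59) if a correlation of 0.1 is assumed, but that too is unstated.

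Three further points are fair:

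- The documents do not themselves cite the 80% to interpret a null result, so the harm is a risk to readers and not a demonstrated misuse.
- The significant between-group results are not overturned by a wrong power statement.
- The reported ANCOVA also adjusts for age and education; the degrees of freedom this costs barely move the 0.73 threshold.

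**Conclusion.** The concern holds. The stated inputs do not produce 60 under any standard reading that uses those inputs alone. For two independent groups at d = 0.5 they produce 128 two-sided or 102 one-sided, assuming equal allocation. Unadjusted two-sided power is 48% at 30 per group and about 50% at the 30 and 33 analysed.

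For the planned ANCOVA, 80% at 30 per group requires a pre/post correlation of about 0.73 two-sided or 0.64 one-sided. At assumed correlations of 0.5, 0.7 and 0.8, two-sided power is 59%, 76% and 89%.

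The finding is that the derivation is wrong as written and the 80% is unsupported. It is not a finding that the ANCOVA was underpowered, which cannot be decided without the missing correlation. Because this is the only basis given for the study's size, it must be corrected.

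**What to change.** Remove the claim that alpha 0.05, power 0.80 and effect size 0.5 give 60. State the test, the sidedness, the allocation ratio and any assumed correlation. Wording that the figures support:

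> Thirty participants per group give 80% power for d = 0.74 in an unadjusted two-sided comparison at alpha 0.05, and about 48% power for d = 0.5. With ANCOVA adjusted for the pre-test score, two-sided power at d = 0.5 is about 59%, 76% and 89% for assumed pre/post correlations of 0.5, 0.7 and 0.8, and reaches 80% at about 0.73.

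If the authors did use a particular correlation or G-power routine, they should give it with its source, so that 60 can be checked.

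Report the adjusted between-group difference with a 95% confidence interval for each outcome in Table 6, and do not read non-significant outcomes as no effect on the strength of the 80% figure.

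The cost is one rewritten paragraph and intervals from the ANCOVA already fitted, with no extra participants and no new data. The price is a less favourable power statement that openly depends on an assumed correlation.
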